## 1. Background

Delirium is an acute brain dysfunction characterized by inattention, disorganized thinking, and a fluctuating course. Delirium is a common complication after surgery, with an incidence up to 70%, depending on patient's age and type of surgery [1]. Patients who experience postoperative delirium is associated with a longer ICU stay, prolonged mechanical ventilation, increased hospital length of stay and health care cost. They also are at increased risk for institutionalization, death, and dementia after hospital discharge. Delirium prevention is expected to reduce morbidity, mortality, hospital length of stay (LOS) and cost, as well as improve the quality of life.

Multiple modifiable and unmodifiable risk factors have been recognized, such as age, type of surgery, ICU admission, pain, and certain medications. Age is a typical example of unmodifiable risk factor. The modifiable risk factors are the targets of delirium prevention. One of the modifiable risk factors is the dosing of sedative or anesthetic agents. Certain features of the intraoperative electroencephalogram (EEG) have been associated with postoperative delirium [2-5]. It was shown that patients with increased low-frequency EEG activity during the rewarming phase of cardiac surgery are at increased risk for postoperative complications, including delirium [2]. EEG burst suppression (BS) is associated with increased incidences of postcoma delirium in ICU patients [3] and postoperative delirium in surgical patients being admitted to ICU after surgery [4].

The advancement of technology allows non-invasive, continuous and convenient EEG monitoring with the adhesive probe placed on patient's forehead. However, the monitor itself is not the goal because pure monitoring without meaningful and effective intervention does not change the outcome. A monitor is valuable only if effective interventions guided by this monitor exist and these interventions improve patient outcome. This principle applies in the clinical use of EEG monitoring. The previous randomized controlled trials investigating the effect of processed EEG – guided anesthetic care on postoperative delirium after general anesthesia was based on the derived number (0-100) provided by BIS monitor. The incidence and duration of EEG burst suppression was not characterized in these studies [6-8]. The characteristic of EEG frequencies, i.e. delta, theta, alpha, and beta, was not reported. In addition, the incidence and character of post-anesthesia care unit (PACU) delirium was not investigated. However, PACU delirium have a strong association with postoperative delirium [9-11].

SedLine® (Masimo, CA) Brain Function Monitoring is an FDA-approved non-invasive EEG monitoring technology. SedLine is different from BIS in many regards. It simultaneously displays four channels of frontal, bilateral EEG waveforms. The Patient State Index (PSI) is a processed EEG parameter that is related to the effect of anesthetic agents (i.e. the popular numeric depth concept). The Density Spectral Array (DSA) provides left and right spectrograms representing the power of the EEG across the frequency range on both sides of the brain. It also provides the burst suppression information (%) and the real-time spectral edge EEG frequency. These parameters are meant to be used in clinical practice to guide anesthesia management.

- 1) Maldonado JR. Delirium in the acute care setting: characteristics, diagnosis and treatment. *Crit Care Clin.* 2008;24(4):657-722

## **2. Purpose of the study**

To investigate the impact of the anesthetic care guided by EEG monitor (SedLine) on (1) the incidence of delirium in post-anesthesia care unit (PACU) and within the first five days after laparoscopic surgery and (2) the incidence of in-hospital complications and 30-day mortality in adult patients after laparoscopic surgery.

## **3. Recruitment of subjects**

Potential participants will be identified within 7 days before the scheduled surgery by the research team.

### **3.1 Inclusion criteria**

- 1) Age  $\geq$  50 years;
- 2) ASA Physical Score I-III
- 3) Scheduled to undergo an elective laparoscopic intra-abdominal surgery under general anesthesia with endotracheal intubation;
- 4) Extubation expected after surgery;
- 5) Scheduled to stay in hospital for  $>$  3 days after surgery.

### **3.2 Exclusion criteria**

Patients will be excluded if they meet any of the following criteria.

- 1) Refuse to participate;
- 2) Emergent surgery;
- 3) Trauma surgery;
- 4) Preoperative history of stroke, schizophrenia, major depression, Parkinson's disease, epilepsy, or dementia;
- 5) Inability to communicate in the preoperative period due to illiteracy, language difficulties, or significant hearing or visual impairment;
- 6) Inability to complete MMSE and delirium survey;
- 7) Severe cardiac disease including low-output cardiac failure defined as a preoperative left ventricular ejection fraction  $<$  30%, or arrhythmia with pacemaker or AICD placement;
- 8) Severe hepatic dysfunction being evaluated for liver transplantation or with a Child-Pugh Class C classification;
- 9) Severe renal dysfunction requiring renal replacement therapy before surgery;
- 10) Those with preoperative ASA classification of 4 or who are unlikely to survive for more than 5 days after surgery.

### **3.3 Criteria of drop out**

- 1) Withdrawal of consent by the participants themselves;
- 2) Procedure converted to open surgery (patients will be followed for intention-to-treat analysis);
- 3) Loss of follow-up (patients may be excluded from per-protocol analysis);
- 4) Ordered to exit by the investigators or attending physicians (occurrence of severe complications or adverse events);
- 5) Cases of unmasked blindness (patients will be excluded from per-protocol analysis);
- 6) Patients who remain intubated after surgery (patients will be excluded from per-protocol analysis).

For drop out cases, the detailed reasons will be recorded and the therapeutic effects recorded in the previous encounter will be regarded as the final results. The Case Report Forms (CRFs) of these cases will be preserved for future reference.

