## 8. Outcome

### 8.1 Primary outcome

Incidence of postoperative delirium during the first 5 days after surgery.

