### **13.3 Patient populations used for analysis**

- 1) The modified intention-to-treat (ITT) population: The modified ITT population includes all patients who undergo randomization, surgery (as long as the skin incision is made), and have the primary outcomes data collected. Patients whose surgery is cancelled or aborted in the middle of surgery (after skin incision) will be included in this population.

The primary outcome is regarded as not collected in the following situations:

- a) death (within postoperative 5 days);
  - b) early hospital discharge (for non-medical reasons and within postoperative 5 days);
  - c) intubated/sedated/comatose for more than 24 hours (within postoperative 5 days);
  - d) withdraw consent (within postoperative 5 days);
  - e) data missing.
- 2) The per-protocol population: The patients from the modified ITT population will be included in the per-protocol population if they fulfill the eligibility, intervention, and outcome assessment specified by the protocol.

The following patients are excluded:

- a) ineligible patients
  - b) randomization allocation error;
  - c) SedLine monitor malfunction (not working at all or >50% of the anesthetic duration (PSI <75) without monitoring data);
  - d) SedLine monitor not blinded in the usual care group;
  - e) being anesthetized with inhalational anesthetics;
  - f) surgery aborted or converted to open.
- 3) As-treated population from the SedLine-guided care group: This population is a subset of the per-protocol population. For patients from the SedLine-guided care group, they are regarded as fulfilling the as-treated criteria if the below-10 SEF AUC (left + right) is less than 10 (or the median value of the AUC, if AUC < 10 gives less than 300 patients). These patients are regarded as having received effective SedLine-guided intervention. This rule does not apply to patients from the per-protocol population from the usual care group.

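### Section 3.3 makes a drop-out's last recorded result final, which scores unassessed days as delirium-free and conflicts with section 13.3

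*Combined protocol and SAP*

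**What the plan says.** The primary outcome in section 8.1 is "Incidence of postoperative delirium during the first 5 days after surgery". Section 7.3(2) schedules two assessments a day through day 5, or to discharge home if that comes sooner, with CAM on the floor and CAM-ICU in the ICU.

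Section 3.3 lists six drop-out situations. Item 1 is "Withdrawal of consent by the participants themselves". Item 2 is "Procedure converted to open surgery (patients will be followed for intention-to-treat analysis", the only item that promises follow-up. Item 4 is "Ordered to exit by the investigators or attending physicians (occurrence of severe complications or adverse events", with no follow-up or analysis clause. Item 6 covers patients still intubated after surgery, with no minimum duration, and removes them from the per-protocol analysis only. A closing sentence then applies to drop-out cases without distinction: "the therapeutic effects recorded in the previous encounter will be regarded as the final results".

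Section 13.3 defines a modified ITT population that requires the primary outcome to have been collected. "The primary outcome is regarded as not collected in the following situations" introduces five items, including (c) "intubated/sedated/comatose for more than 24 hours (within postoperative 5 days", (d) "withdraw consent (within postoperative 5 days", and (e), missing data, which is not defined further. Section 13.3 has no carry-forward rule and does not refer to 3.3. Neither section says which takes precedence.

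**The concern.** An outcome of any delirium in five days can be called negative only when the window has been observed. If the last result is final, a patient who leaves on day 2 with negative assessments counts as free of delirium through day 5, although days 3 to 5 were never examined.

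Section 13.3 handles some of the same patients differently. For them the plan gives two answers, and the choice could be made after the data are seen. Patients with a severe complication are plausibly at higher risk of delirium, so the rule for them should be settled in advance.

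**Working it through.** **1. The two sections side by side.**

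- *Consent withdrawn within 5 days.* Under 3.3(1) the last result is final and the patient is analysed. Under 13.3(d) the outcome was not collected and the patient leaves the population. This contradiction needs no inference. It works in both directions: a patient who is CAM-positive on day 1 and withdraws on day 2 is a case under 3.3 and absent under 13.3.
- *Intubated after surgery for 24 hours or less.* Under 3.3(6) the patient is a drop-out whose result is fixed at the previous encounter. Under 13.3(c) the patient remains evaluable.
- *Ordered to exit.* Section 7.3(2) implies that assessment continues to day 5 or discharge. Section 3.3(4) does not say so, and the last-result rule points the other way. Item 13.3(e) applies only if assessment actually stops and a partly observed window counts as missing.

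**2. The plan's own figure.** Section 4.2 gives p1 = 0.14, a one-third reduction (p2 = 0.0933), two-sided alpha 0.05 and 80% power. With mean rate p̄ = 0.1167,

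n = [1.96·√(2p̄(1−p̄)) + 0.8416·√(p1(1−p1) + p2(1−p2))]² / (p1−p2)² = 741.7, so 742 per arm, as stated.

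742 × 1.05 = 779.1, which rounds up to 780. The same pooled-variance test has 80.0% power at 742 and 81.9% at 780.

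**3. Assumptions for size.** The documents give no exit rate. Let f be the share in each arm who exit before any positive assessment (1-5%) and r the later delirium risk among them in control (20-40%). True overall rates stay at 0.14 and 0.0933, and assessment is assumed to stop at exit. Control cases lost at 780 are 780·f·r, from 780 × 0.01 × 0.20 = 1.6 to 780 × 0.05 × 0.40 = 15.6, out of 780 × 0.14 = 109.2.

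**4. Later risk in the intervention arm two-thirds of control.** Carried-forward rates are 0.14 − fr and 0.0933 − 2fr/3, so the RR stays 0.667. Exclusion divides both rates by (1 − f) and multiplies n by (1 − f), with the same RR.

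| f, r | Power at 780, carried forward | Power at 780, excluded |
|---|---|---|
| 1%, 20% | 81.3% | 81.4% |
| 2%, 30% | 80.0% | 80.1% |
| 5%, 30% | 76.9% | 77.2% |
| 5%, 40% | 75.0% | 75.3% |

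If exits come on top of the 5% loss allowance (742 per arm), power falls from 80.0% to 79.4-72.9% carried forward, or 79.4-73.1% excluded. The two handling rules differ by at most about 0.3 percentage points.

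**5. Equal later risk in both arms.** The intervention rate becomes 0.0933 − fr. At f = 1%, r = 20% the recorded RR is 0.0913/0.138 = 0.662. At f = 5%, r = 40% it is 0.0733/0.12 = 0.611. Power at 780 rises to 82.5-87.7%, but only because the recorded effect is larger than the true 0.667.

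**6. Unequal exits with no true effect.** Take both arms at 0.14, exits of 2% in intervention and 4% in control, and r = 30%. Carried forward, the rates are 0.14 − 0.02 × 0.30 = 0.134 and 0.14 − 0.04 × 0.30 = 0.128, so RR = 1.05. Excluded, RR = (0.134/0.98)/(0.128/0.96) = 1.03. Two-sided rejection at 780 is 6.4% or 5.4% instead of 5%.

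**The case against.** The strongest reply is that a drop-out under 3.3 is not a patient whose follow-up ends. Open conversions are drop-outs and are followed. Items 5 and 6 affect only the per-protocol analysis and also lack a follow-up clause, so silence in item 4 is weak evidence that assessment stops. Severe complications feed secondary outcomes to day 30, and the serious adverse event form allows the study protocol to continue. The EEG intervention is over by the end of surgery, so a postoperative exit has little left to stop. Postoperative assessors are blinded, which makes unequal exits less likely. All of this stands, and continued assessment was probably intended. It does not remove the last-result sentence or the contradiction on consent withdrawal.

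A reader might infer more than the documents support:

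- *That 13.3(e) excludes patients ordered to exit.* Section 13.3 never names them. Item (b) covers early discharge only when it is for non-medical reasons, so an incomplete window is not automatically missing.
- *That section 10.2 ends assessment after a severe adverse event.* Sections 5.2 and 9.2 use the term study protocol for the anesthesiologist's care. The study flow chart runs protocol execution to day 30, so a clarifying word would help, but this is not a separate error.
- *That equal exits leave the RR alone and cost only power.* That follows from the two-thirds assumption in step 4. Step 5 shows otherwise.

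**Conclusion.** Wrong as written, minor severity. The last-result rule does not suit a cumulative five-day outcome. It contradicts 13.3 outright for consent withdrawal and is inconsistent with it for short intubation. For ordered exits the defect is an unstated rule, not a demonstrated loss of assessments.

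The size is unknown and probably small. The upper end of the range needs 5% ordered exits, equal to the whole loss allowance in 4.2, with 40% later delirium and assessment actually stopping. At 2% exits and 30% later delirium, under the two-thirds assumption, power at 780 is still 80.0%. The direction is not established: the effect is a loss of power if later risk follows the treatment effect, and an overstated benefit if later risk is equal. Choosing between carry-forward and exclusion changes little under equal exits. What matters more is whether assessment continues.

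**What to change.** Make three wording changes.

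1. In 3.3, remove the last-result rule for the delirium outcome and use the observed assessments.
2. State that 13.3 alone governs patients who lack outcome data.
3. In 3.3(4), state that an ordered exit stops only the study intervention and the protocol's care restrictions. Unless consent is withdrawn, twice-daily CAM or CAM-ICU to day 5 or discharge and the day-30 contact continue.

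Optionally, say study intervention in place of study protocol in 10.2.

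The cost is a short amendment, with no change to the sample size. The downside is that a few sicker patients go on being assessed, by blinded staff who are already scheduled to visit twice a day.

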### **3.4 Criteria of Rejection**

Enrolled cases who meet any of the following criteria will be excluded from further per-protocol analysis.

- 1) Intervention protocol is not executed;
- 2) No or incomplete study record;

Enrolled cases who meet any of the following criteria will be excluded from further as-treated analysis.

Unable to evaluate the effectiveness of intervention (e.g., missing SedLine data).

For rejected cases, the detailed reasons will be recorded and CRFs will be preserved for reference. The results of these cases will be excluded in analysis of therapeutic effects.

### **3.5 Criteria of Study Interruption**

Study will be interrupted in the following situations:

- 1) Severe safety issues occurred during the study;
- 2) Serious mistakes found in the protocol;
- 3) Fund or management problem of the investigators;
- 4) Study terminated by the administrative authority.

Study interruption may be transient or permanent. All recorded CRFs will be preserved for reference in case of study interruption.

## **4. Study design**

### **4.1 Type of the study**

The study is a prospective, double blinded, randomized and controlled parallel trial. (The only people who know the patient's assignment are the study coordinator and the anesthesia team who takes care of the patient during surgery.)

### **4.2 Sample size calculation**

The incidence of postoperative delirium is about 14% in elderly patients who underwent laparoscopic surgery for colorectal cancer [Tei et al., 2016]. We assume that the incidence of postoperative delirium will be reduced by 1/3 in patients receiving EEG-guided care [Chan et al., 2013]. With a two-sided significance and power set at 0.05 and 80%, respectively, the sample size required to detect the reduction is 742 patients per group. Taking into account a loss-to-follow-up rate of about 5%, we plan to enroll 780 patients in each group.

## **5. Randomization and blinding**

### **5.1 Randomization**

- 1) A biostatistician who does not participate in data management and statistical analysis will generate random numbers in a 1:1 ratio;
- 2) The results of randomization will be sealed in sequentially numbered envelopes, stored at the site of investigation, and managed by the study coordinator.
- 3) Timing of randomization of individual patient: 30-60 mins before surgery

### **5.2 Blinding**

- 1) A study coordinator will be assigned to distribute the EEG monitor, open the randomization envelope, inform the anesthesiologist of the patient's assignment, enforce the execution of the study protocol, collect the data during surgery, and coordinate the overall research effort;
- 2) For each recruited patient, the anesthesiologist is one of the two persons who know the patient assignment. The other person is the study coordinator who opens the randomization envelope. The anesthesiologist will be instructed of how to use the EEG monitor to guide the anesthesia care per research protocol if the patient is assigned to the intervention arm;
- 3) For each recruited patient, the study coordinator is the only research team member who comes to the Operating Room to monitor the execution of the study protocol;
- 4) Two research personnel, different to the study coordinator, will be responsible for postoperative follow-up including delirium assessment starting at the post-anesthesia care unit. These two personnel are blinded to patient randomization;
- 5) The anesthesiologist who executes the study protocol and the research personnel who collects postoperative outcome data do not share any information related to patient assignment;
- 6) Statistical analysis will be performed independently by the designated statistician at Yale University.

## **6. Intervention protocol**

### **6.1 Monitor used in the intervention group**

- 1) Name: SedLine Brain Function Monitoring;
- 2) Product specification: FDA-approved non-invasive EEG monitor;
- 3) Manufacturer: Masimo Corporation, Irvine, CA.

### **6.2 Monitor used in the control group**

- 1) Name: SedLine Brain Function Monitoring;

- 2) Product specification: FDA-approved non-invasive EEG monitor;
- 3) Manufacturer: Masimo Corporation, Irvine, CA.

### **6.3 Monitoring**

- 1) All recruited patients from either control or intervention group will receive SedLine EEG monitoring;
- 2) A study coordinator will distribute the monitor 30 mins before the arrival of the patient in the Operating Room;
- 3) The probe of SedLine monitor will be placed on patient's forehead after the patient's arrival in the Operating Room and before the anesthesia induction;
- 4) The monitor data will be collected by the study coordinator.

### **6.4 Anesthetic care guided by EEG monitoring**

- 1) The monitor screen in the control arm is covered and blinded to the anesthesiologist;
- 2) The monitor in the intervention arm is used by the anesthesiologist to adjust the anesthetic care.
- 3) The goal in the intervention arm is to maintain SEF 10-15 throughout surgery. Avoid burst-suppression.
- 4) In the intervention arm, the anesthesia induction is achieved via propofol pump infusion (slow and controlled). The goal is to avoid burst-suppression and maintain SEF > 10 throughout anesthesia induction.
- 5) The anesthesia maintenance is achieved via the protocol detailed below (6.5). The SedLine-guided intervention protocol is detailed in the **Supplemental remark 1. SedLine-Guided Intervention Flow Chart**.

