## 7.3 Postoperative data

- 1) PACU Delirium: Occurrence of delirium in PACU will be assessed using the CAM-ICU 30 mins after extubation and before PACU discharge.
- 2) Postoperative Delirium (POD): POD will be assessed twice daily (8:00-10:00 am, and 18:00-20:00 pm) for 5 days from postoperative day 1 to 5 or until the patient is discharged home if the patient stays in hospital < 5 days. CAM is used for delirium assessment if the patient is on the floor; otherwise, CAM-ICU is used if the patient is in the ICU. Investigators for POD assessment will be trained by a psychiatrist to use CAM and CAM-ICU before the trial is commenced.
- 3) Non-delirium Complications: Any complications occurred within the first 30 days after surgery (for example: cardiac events, cerebrovascular events, renal injury, GI complications, infections, etc.) will be documented. Patients will be assessed via phone call if they are discharged before day 30 after surgery.
- 4) Subjective Pain Score: It will be assessed at PACU and 24 hours after surgery using the Numeric Rating Scale (NRS) (an 11-point scale where 0 indicates no pain and 10 indicates the worst pain).
- 5) Subjective Sleep Quality: It will be assessed at 8:00 am during the first postoperative day using the NRS (an 11-point scale where 0 indicates the best possible sleep and 10 indicates the worst possible sleep).
- 6) Length of Hospital Stay: The readiness for discharge will be used as the last day of hospitalization.
- 7) All-cause 30-day Mortality: Patients or family members will be called for assessment.
- 8) Adverse Events: If an adverse event occurs during patient hospitalization, it will be followed up until its disappearance or therapy ends.

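### Only the control screen is covered, and pump induction is specified only for the SedLine arm, so the described procedures do not secure the double blind claimed in 4.1

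*Combined protocol and SAP*

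**What the plan says.** Section 4.1 describes a double-blinded trial and states: "The only people who know the patient's assignment are the study coordinator and the anesthesia team who takes care of the patient during surgery". Section 5.2 item 2 is narrower. It names two persons, the anesthesiologist and the coordinator who opens the envelope.

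On the monitor, Section 6.3 says "All recruited patients from either control or intervention group will receive SedLine EEG monitoring", and on timing: "The probe of SedLine monitor will be placed on patient's forehead after the patient's arrival in the Operating Room and before the anesthesia induction". Section 6.4 then treats the arms differently. For control, "The monitor screen in the control arm is covered and blinded to the anesthesiologist". For the other arm, "The monitor in the intervention arm is used by the anesthesiologist to adjust the anesthetic care".

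Sections 6.4 (item 4) and 6.5 (item 2) also specify propofol induction by pump, guided by SedLine, for the intervention arm only. Both arms otherwise share the same list of induction agents.

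On follow-up, Section 5.2 assigns delirium assessment to two people other than the coordinator, blinded and starting in the PACU. For length of stay, Section 7.3 says: "The readiness for discharge will be used as the last day of hospitalization".

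**The concern.** Every patient has the same device, so whether its screen is covered is equivalent to the allocation for anyone who knows the design. The cover is described only as a blind for the anesthesiologist. The surgical team works in the same room, and Section 5.2 contains no measure directed at them, at the operating-room nurses or at the patient. Pump induction is a second cue of the same kind.

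What is at stake is the credibility of some secondary results. Section 8.2 includes length of stay, ICU admission and a composite of Clavien-Dindo grade II or higher. Grade II is itself defined by treatment given, and many of the listed complications count only once treated. If the clinicians who make those decisions know the arm, a between-group difference could partly reflect that knowledge. Pain and sleep scores (Section 8.3) come from the patient. A report that carries the double-blind label would hide this limitation.

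**Working it through.** No figure in the plan bears on this point, and the sample size in Section 4.2 does not depend on it. The check sets the sections side by side.

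**Step 1: does anything observable differ by arm?** Device and forehead probe do not differ (6.1 to 6.3). The screen differs: covered in control, in use in the SedLine arm (6.4 items 1 and 2). Induction by pump is specified for one arm only (6.4 item 4, 6.5 item 2).

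**Step 2: when could it be observed?** Randomization is 30 to 60 minutes before surgery (5.1). The probe goes on before induction (6.3 item 3). Because induction in the SedLine arm is guided by the monitor, the arm must be known by the time induction starts, when the patient is still awake. The plan does not say when the cover is fitted, how, or which way the screen faces.

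**Step 3: which groups does a described measure protect?**

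| Group | Status under 4.1 and 5.2 | Measure described |
|---|---|---|
| Delirium assessors | Stated to be blinded | Separate from the coordinator; no sharing of assignment with the anesthesiologist; the coordinator is the only research team member in the operating room (5.2 items 3 to 5) |
| Surgeons, operating-room nurses | Unaware, by implication of 4.1 | None |
| Patient | Unaware, by implication of 4.1 | Same device and probe in both arms; nothing on the cover or the pump |
| PACU and ward staff | Unaware, by implication of 4.1 | None |

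**Step 4: do other sections close the gap?** Section 3.3 item 5 lists unmasked cases as drop-outs and excludes them from the per-protocol analysis. Section 13.3 excludes control patients whose monitor was not blinded. Both act after a failure. Neither stops a surgeon or nurse from inferring the arm when the cover is used exactly as planned.

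**Step 5: which outcomes are exposed?** The primary CAM or CAM-ICU rating is made by the protected group. Readiness for discharge, ICU admission and treatment-defined complications may rest on unprotected groups, but the plan does not say who decides them.

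**Step 6: can the size be calculated?** No. The documents give no rate of unblinding, no blinding check, and neither a standard deviation nor an expected shift for length of stay.

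**The case against.** The strongest reply is that exposure is not shown. A reader might infer that surgeons and patients actually see the allocation. The documents do not support that: sightlines, the timing of the cover and what bystanders are told are not described. The patient limb is the weakest. The probe is identical in both arms, and a patient would also have to know that a covered screen means control. The consent pages are not available, so what patients are told cannot be judged. This part stands, and the point is therefore that concealment is not secured, not that it fails.

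A reader might also carry the concern over to the primary outcome, since CAM Feature 1 is usually obtained from a nurse or family member. Nothing shows that those informants learn the arm, and the raters themselves are separated from the operating room.

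A third temptation is to attach an inflated false-positive rate to length of stay. That would need an assumed standard deviation and shift. It would also not describe this trial's tests, which are Wilcoxon or log-rank (13.5) with Benjamini-Hochberg control across secondary outcomes (13.1).

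Finally, 4.1 already implies that surgical and ward staff are not told. Not telling them is different from preventing them from inferring the arm, so this reply only partly answers the point.

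**Conclusion.** The point holds in a limited form. The double-blind statement in 4.1 claims more than the procedures in 5.2, 6.4 and 6.5 deliver, because two arm-specific cues are left unconcealed from operating-room staff outside the anesthesia team and possibly from the awake patient. Sections 4.1 and 5.2 also disagree on who knows the assignment.

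The concern is confined to secondary outcomes that may depend on treating clinicians and, more speculatively, to patient-reported scores. Its size is unknown. It rests on two assumptions that the documents neither state nor exclude: that others in the room can see and interpret the cues, and that people who learn the arm influence discharge, ICU or treatment decisions. The change is worth making because it is nearly free and corrects a stated property of the design.

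**What to change.** - **6.4:** fit the same opaque shield to the screen in both arms before the patient enters the operating room. In the SedLine arm it is viewable only from the anesthesiologist's position; in the control arm it is closed.
- **5.2:** state that surgical, PACU and ward staff and the patient are not told the arm. Reconcile the two-person wording with the anesthesia team named in 4.1.
- **3.3 item 5:** record any disclosure under the existing category for unmasked cases. As written, that category is a drop-out with the last recorded result taken as final, so add that these patients continue full follow-up and stay in the modified ITT population.
- **4.1:** the shield does not hide the induction difference, so replace the double-blind label with an exact statement of who is blinded, at minimum the delirium assessors.
- **Reporting:** present length of stay and ICU admission as outcomes decided by clinicians whose blinding was not assured.

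The cost is one shield per monitor, short edits to these sections, slightly less convenient viewing for the anesthesiologist and a weaker blinding label. Sample size, visits and staffing are unchanged.
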